6.11.3. Pump Factors

Actual and change from baseline in pump factors affecting insulin dosing, including breakfast CR, AIT, breakfast ISF, and frequency of use of non-normal bolus type (Square wave or Dual Wave), will be summarized and compared between LY900014 and insulin lispro using an MMRM models as specified in Section 6.1.

For each patient, frequency of use of non-normal bolus type at a visit will be calculated as the total number of meal-related bolus doses given as Square Wave or Dual Wave during the 7 days prior to the visit date divided by the total number of meal-related bolus doses during the 7 days prior to the visit date.

A listing of these pump factors will also be provided, including data collected at Visit 801.

6.11.4. Extent of Exposure

Duration of exposure to study drug will be summarized. The following summary statistics will be provided: n, mean, SD, median, minimum, maximum, and sum (that is, total patient-years of exposure). The number and proportion of patients falling into the following different exposure categories will also be summarized: <7 days (>0 and <7 days), ≥ 7 and <14 days, ≥ 14 and <28 days, ≥ 28 days and < 42 days) and ≥ 42 days.

Patients who complete the study treatment period are required to complete a safety follow-up visit without study drug; and patients who discontinue the IP prematurely are required to discontinue from the study (ITSI Protocol 8.1-8.2).

6.11.5. Adverse Events

Events that are newly reported after the first dose of rapid-acting insulin provided as study drug (i.e., open-label insulin lispro used during the lead-in period or IP used during each of the two 6-week randomized treatment periods) or are reported to worsen in severity from baseline (defined

in [Table ITSI.6.6](#) for each specific study period) will be considered TEAEs. Events that continue during more than 1 study period (lead-in, Period I, Period II) with the same severity will only be counted once for the first study period.

The Medical Dictionary for Regulatory Activities (MedDRA) lowest level term (LLT) will be used in the treatment-emergent assessment. The maximum severity for each LLT during the baseline period will be used as baseline severity. For events occurring on the day of first dose of blinded bolus insulin provided in this study during each treatment period (lead-in, Period I and Period II), the CRF-collected flag will be used to determine whether the event started or worsened post-treatment, and/or the treatment of which period the AE should be assigned.

In an overview table, the number and percentage of patients who experienced a TEAE, experienced serious adverse event (SAE), died due to an AE, and discontinued from study due to an AE will be summarized.

The number and percentage of patients with SAEs and who discontinued from the study due to an AE will be summarized using MedDRA Preferred Term (PT) nested within System Organ Class (SOC). Prescott's exact test will be performed for treatment comparison.

The number and percentage of patients with TEAEs (overall and by possible relatedness: related to study disease, study drug, study procedure or study device) will be summarized by treatment using MedDRA PT nested within SOC. Events will be ordered by decreasing frequency within SOC. As an additional table, the percentages of patients with TEAEs will be summarized by treatment using MedDRA PT (without regard to SOC). Events will be ordered by decreasing frequency in total group. Statistical comparisons will be applied at both the SOC and PT levels. Prescott's exact test will be performed for treatment comparison.

The number and percentage of patients with TEAEs by maximum severity will be summarized by treatment using MedDRA PT (without regard to SOC). For each patient and TEAE on each treatment, the maximum severity for the MedDRA PT is the maximum postbaseline severity observed from all associated LLTs mapping to the MedDRA PT during the corresponding randomized treatment period for the specified treatment. No statistical comparison between treatment groups will be conducted.

The number and percentage of patients who experienced a SAE including deaths and SAEs temporally associated or preceding deaths will be summarized by treatment group using MedDRA PT (without regard to SOC). Events will be ordered by decreasing frequency within SOC. A listing of all SAEs (including data collected during the safety follow-up period) will also be provided.

The number and percentage of patients who discontinued from study in Period I and Period II due to an AE will be summarized by treatment group using MedDRA PT (without regard to SOC). Events will be ordered by decreasing frequency. A listing of all AEs as reason for study discontinuation will also be provided.

For events that are gender-specific (as defined by MedDRA), the denominator and computation of the percentage will include only patients from the given gender.

Table ITSI.6.5 summarizes the planned analyses and the requirement of analysis data for different analysis periods.

Table ITSI.6.5. Adverse Event Analysis Periods

Analysis Period	Analysis Population	Analysis	IP USE	Treatment
Lead-in Period	All Enrolled Patients	AE overview; TEAE by PT; SAE, discontinuation due to AE	N/A	Open-label insulin lispro
Treatment Period (0-12 Weeks)	Safety Population	AE overview; TEAE by SOC and by PT; TEAEs by maximum severity; SAE; discontinuation due to AE; other notable AEs	All data regardless of IP use	LY900014, insulin lispro
Safety Follow-up Period	All Patients in the Safety Population who enter follow-up period	TEAE by PT	All data	Overall ^a

Abbreviations: AE = adverse event; IP = investigational product; N/A = not applicable/available; PT = preferred term; SAE = serious adverse event; SOC = system organ class; TEAE = treatment-emergent adverse event

Note: ^a overall means that data will be summarized in total and no by-treatment group summary or statistical analysis will be included.

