GCP	good clinical practice
HbA1c	hemoglobin A1c
IB	Investigator's Brochure
ICF	informed consent form
ICH	International Conference on Harmonisation
IP	investigational product: A pharmaceutical form of an active ingredient or placebo being tested or used as a reference in a clinical trial, including products already in the market when used or assembled (formulated or packaged) in a way different from the authorized form, or marketed products used for an unauthorized indication, or marketed products used to gain further information about the authorized form.
ISF	insulin sensitivity factor
IWRS	interactive web-response system
LLT	lowest level term
LS	least squares
MDI	multiple daily injections
MedDRA	Medical Dictionary for Regulatory Activities
MMRM	mixed-effect model repeated measure
PPG	postprandial glucose
product complaint	Product complaints are a customer's written, electronic, or oral communication that alleges deficiencies related to the identity, quality, durability, reliability, safety, effectiveness, or

	performance of a Lilly product after it is released for distribution.
PT	preferred term
SAE	serious adverse event
SAP	statistical analysis plan
screen	The act of determining if an individual meets minimum requirements to become part of a pool of potential candidates for participation in a clinical study.
SD	standard deviation
SMBG	self-monitored blood glucose
SOC	system organ class
SUSARs	suspected unexpected serious adverse reactions
T1DM	type 1 diabetes mellitus
T2DM	type 2 diabetes mellitus
TBL	total bilirubin level
TEAE	treatment-emergent adverse event: An untoward medical occurrence that emerges during a defined treatment period, having been absent pretreatment, or worsens relative to the pretreatment state, which does not necessarily have to have a causal relationship with this treatment.
ULN	upper limit of normal
unexplained hyperglycemia	High blood glucose that cannot be explained by a missed prior bolus, dietary indiscretion, rebound or treatment of hypoglycemia, a pump failure, an empty pump reservoir, an infusion set complication (for example, kinked, came out, leaking), or an infusion site complication (for example, pain, redness).

---

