Pump factors - breakfast CR, AIT, breakfast ISF)	All Patients in the Safety Population with a baseline and at least one post-baseline observation	Visit 3 prior to the first dose of IP excluding data (if any) that are collected while patients temporarily are off pump or off open-label insulin lispro	Visits 4, 6, 7, and 9 prior to last dose in IP of each randomized treatment period (Period I and Period II) excluding data (if any) that are collected while patients temporarily are off pump or off IP
Pump factor - frequency of use of non-normal bolus type [Square Wave or Dual Wave] ³	Population with a baseline and at least one post-baseline observation	Visit 3	Visit 4, 6, 7, 9
12-Week Treatment Period Regardless of IP use (from randomization to Week 6 of each randomized treatment period regardless of IP use)			
TEAEs	All Patients in the Safety Population	Prior to first dose of randomized IP (or Visit 3 if the dose date is missing) but after the first dose of open-label insulin lispro in the lead-in period	From randomization to Week 6 of each randomized treatment period regardless of IP use
Weight and vital signs	All Patients in the Safety Population with a baseline and a post-baseline observation	Last of Visits 2-3	Visits 4, 6, 7, and 9 regardless of IP use
Safety Follow-Up Visit (Overall¹ Only)			
TEAEs	All Patients in the Safety Population who enter the safety follow-up period	After first dose of IP and prior to last dose of IP in the 12-Week Treatment Period	From the date of the last visit of the 12-Week treatment period to the end of study
Weight and vital signs	All Patients in the Safety Population who enter the safety follow-up period	Last of Visits 2-3	Visits 801

Abbreviations: 1,5-AG = 1,5-Anhydroglucitol; CGM = Continuously Glucose Monitoring; CR = carb ratio; HbA1c = hemoglobin A1c; IP = investigational product; MMRM = mixed-effect model repeated measures; SMBG = self-monitored blood glucose; TEAE = treatment-emergent adverse event

Note:

- ¹ Overall means that data will be summarized in total and no by-treatment group summary or statistical analysis will be included.
- ² Not required for the interstitial glucose reduction rate and duration of each individual hypoglycemic episode because it is possible that some patients may not have any non-meal related correction bolus or hypoglycemic event to baseline values.

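### The rule that counts a continuing AE once covers only unchanged severity and the lead-in is the only TEAE baseline, so an AE easing after the crossover may be counted under both insulins

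*SAP*

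**What the plan says.** Four statements in the SAP decide how an AE that spans the crossover is counted.

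- **What makes a TEAE (6.11.5).** There are two routes. One is "Events that are newly reported after the first dose of rapid-acting insulin provided as study drug". The other is a reported worsening in severity from the baseline of the period concerned. For that baseline the text points to Table ITSI.6.6, which is the table of hypoglycemia methods. The TEAE baselines are in Table ITSI.6.2.
- **The baseline (Table ITSI.6.2, section 6.1).** One row serves both randomized periods. Its baseline is "Prior to first dose of randomized IP (or Visit 3 if the dose date is missing) but after the first dose of open-label insulin lispro". This window is the lead-in. Its post-baseline window runs "from randomization to Week 6 of each randomized treatment period regardless of IP use". Period II has no separate baseline.
- **Baseline severity (6.11.5).** "The maximum severity for each LLT during the baseline period will be used as baseline severity".
- **Continuing events (6.11.5).** The rule is "Events that continue during more than 1 study period (lead-in, Period I, Period II) with the same severity will only be counted once". The single count goes to the earliest of the periods concerned.

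The protocol glossary (Appendix 1) describes a TEAE as one that "emerges during a defined treatment period, having been absent pretreatment, or worsens relative to the pretreatment state". The design has no washout between periods. TEAEs are compared between insulins by Prescott's exact test at SOC and PT level. Infusion site reactions and potential systemic hypersensitivity reactions are drawn from the TEAEs and tested in the same way (SAP 6.11.7.2 and 6.11.7.3).

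**The concern.** Take an AE that is absent in the lead-in, moderate in Period I, and mild but ongoing in Period II. Against the lead-in baseline it is still worse than baseline in Period II. Its severity has changed, so the sentence on continuing events does not cover it. Applied as written, the rules can then make it a TEAE of the second insulin, although it arose on the first and was resolving.

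Prescott's test takes its information from patients whose outcome differs between the two periods. Recounting turns such a patient from one-treatment to both-treatments, and the patient then contributes no difference. The recount falls on whichever insulin comes second, so the effect is dilution of a real difference. In a trial meant to assess safety comparability, that is the unwelcome direction.

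A second consequence is practical: two programmers working from the same SAP could produce different TEAE tables.

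**Working it through.** **The plan's own figure.** The nearest stated number is the sample size: 42/(1 − 0.12) = 47.7, rounded up to 48. It reproduces, and this point does not affect it.

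**Which AEs are exposed.** I assumed a three-grade severity scale (1 mild, 2 moderate, 3 severe; 0 = absent) and wrote each AE as lead-in maximum / Period I / Period II. I kept the patterns that are treatment-emergent in Period I (Period I above lead-in) and continue at lower severity (Period II at least 1 and below Period I). There are eight.

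- Literal rule: count in Period II if severity exceeds the lead-in maximum and differs from Period I.
- Amended rule: count in Period II only if severity exceeds the maximum of lead-in and Period I.

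| Pattern | Counted again, literal rule | Counted again, amended rule |
|---|---|---|
| 0/2/1 | yes | no |
| 0/3/1 | yes | no |
| 0/3/2 | yes | no |
| 1/3/2 | yes | no |
| 1/2/1 | no | no |
| 1/3/1 | no | no |
| 2/3/1 | no | no |
| 2/3/2 | no | no |

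The literal rule recounts 4 of 8 patterns, including all 3 in which the AE was absent in the lead-in. The amended rule recounts none. These are counts of patterns, not of patients.

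**What a recount does to the test.** Inputs: 42 completers (SAP 5.2), taken as 21 per sequence, and two-sided alpha 0.05 (SAP 6.1). Event counts are assumed.

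Score each patient +1 for an event in Period I only, −1 for Period II only, and 0 for both or neither. Let a, b and c be the numbers scoring +1, 0 and −1, and let T be the score total in Sequence A (LY900014 first). With i, j, k the numbers of each score allocated to Sequence A (i + j + k = 21), each allocation has probability C(a,i)·C(b,j)·C(c,k)/C(42,21). Sum these over allocations where |i − k − E| ≥ |T − E|, with E = 21(a − c)/42.

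*Illustration 1: events on LY900014 only, 3 patients per sequence (6 versus 0).* Here a = 3, b = 36, c = 3, T = 3 and E = 0. Only the most extreme allocation and its mirror image qualify, so p = 2 × C(36,18)/C(42,21) = 2 × 0.01686 = 0.034. If one Sequence A patient is recounted under lispro, a = 2, b = 37, c = 3 and p = 0.066. If two are recounted, p = 0.125.

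Other starting counts, with 0, 1 and 2 Sequence A patients recounted (Sequence A and Sequence B events in brackets):

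| LY900014 only | 0 | 1 | 2 |
|---|---|---|---|
| 5 (3 and 2) | 0.066 | 0.131 | 0.256 |
| 6 (3 and 3) | 0.034 | 0.066 | 0.125 |
| 7 (4 and 3) | 0.017 | 0.034 | 0.066 |
| 8 (4 and 4) | 0.009 | 0.017 | 0.032 |

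*Illustration 2: in each sequence, 6 patients with the event on LY900014 only and 1 on lispro only (12 versus 2).* Of the six Sequence A patients with LY900014 events, m are recounted:

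| m | Difference in incidence | p |
|---|---|---|
| 0 | 10/42 = 23.8 points | 0.014 |
| 2 | 8/42 = 19.0 points | 0.040 |
| 3 | 7/42 = 16.7 points | 0.066 |
| 6 | 4/42 = 9.5 points | 0.265 |

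**The case against.** **The SAP nowhere says that an improving AE is counted twice.** A reader might infer that it prescribes this; it does not. An AE that began in Period I is not newly reported in Period II, and nobody would report it as worsening. The glossary asks that a TEAE emerge during the treatment period. The intent of the continuing-event sentence is plainly to count once. This stands, and it makes the point an ambiguity. It does not close the gap. The worsening route is measured against the lead-in. If continuing AEs could never count in Period II, a clause limited to unchanged severity would hardly be needed for that transition. The CRF flag on period assignment covers only events on the day of first dose.

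**Protocol and SAP may seem to contradict each other on what a TEAE is.** That goes too far. The glossary does not say that the pretreatment state for Period II is the end of Period I, and protocol 10.3.3.2 defines TEAEs much as the SAP does.

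**Not every AE that continues at lower severity is exposed.** Correct: one that falls to or below its lead-in maximum is not recounted on any reading.

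**The trigger may never be recorded.** If each AE carries a single severity throughout, its severity is always unchanged and the existing sentence catches it. The documents do not settle this.

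**The illustrations cross 0.05 because of the counts chosen.** True in part. At 5 versus 0 the test is non-significant from the start, and at 8 versus 0 it survives two recounts. One or two of the three Sequence A patients is a large fraction with no support in the documents. For overall TEAE incidence, a patient with any other Period II TEAE is unaffected by the recount.

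**The stakes are limited.** AEs are a tertiary/exploratory objective, tested without multiplicity adjustment, in a trial stated not to be powered for non-inferiority or superiority. This stands.

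**Conclusion.** The point holds as a gap in the counting rules. Read literally, they may count an AE under both insulins when three conditions are met: it started or worsened in Period I, it continues into Period II at lower severity, and that severity still exceeds the lead-in maximum. The documents equally permit the reading under which it counts once.

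The direction, if the literal reading is programmed, is dilution of TEAE comparisons toward no difference. Each affected patient adds 1/42 = 2.4 percentage points to the second insulin's incidence, provided that patient has no other Period II event in the same category. The total is unknown, because the documents give neither the frequency of such AEs nor evidence that a downgrade is recorded separately. The p-values show how sensitive a test of this size is to one or two patients; they do not estimate bias in this trial.

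The TEAE tables and the analyses drawn from them are affected. The primary endpoint and the sample size are not. The wrong table reference needs correcting on either reading.

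**What to change.** Three edits to the SAP:

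1. In 6.11.5, extend the once-only clause from events continuing at the same severity to those continuing at the same or lower severity.
2. In Table ITSI.6.2, state that for an AE ongoing at the first Period II dose, baseline severity is its maximum over the lead-in and Period I. It then counts in Period II only if it worsens beyond that.
3. In 6.11.5, change the baseline cross-reference from Table ITSI.6.6 to Table ITSI.6.2.

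The cost is a phrase, a table entry and a table number, with slightly more programming. SAP version 3 already revised the TEAE baseline for the randomized periods before unblinding, so an edit of this kind is practicable. The study team should also confirm how severity changes in ongoing AEs are recorded. If only one severity is kept per AE, the edits alter no counts but still remove the ambiguity.

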## 8. Discontinuation Criteria

### 8.1. Discontinuation from Study Treatment

Patients who need to discontinue from study treatment will also be discontinued from the Study. Please refer to Section 8.2.

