Serious adverse events, AEs reported as reason for discontinuation from the IP or study, and TEAEs will be summarized in tables using the MedDRA PT, sorted by decreasing frequency within the LY900014 treatment group. TEAEs will also be summarized by PT sorted by decreasing frequency within SOC for all TEAEs and by maximum severity. For events that are specific to only 1 sex, the denominator and computation of the percentage will include only patients from the given sex. The number and proportion of patients with at least 1 event for each type of event will be summarized and compared between treatment groups using Prescott's test. SAEs, AEs reported as reason for discontinuation from the study, and TEAEs will also be summarized for open-label insulin lispro during the lead-in period.

If there are  $\geq 10$  patients with severe hypoglycemic event, the proportion of patients with at least 1 severe hypoglycemic event (incidence) after randomization will be analyzed using a generalized linear mixed model with options of the binomial distribution and logit link function. The model will include treatment, period, and sequence. The within-patient error will be modeled as the compound symmetry variance-covariance matrix. Prescott's exact test will be conducted as sensitivity analyses.

Both date and time of all infusion set changes will be captured and time interval until infusion set change will be derived through a minute-to-hour conversion.

The interstitial glucose reduction rate within 4 hours following a non-meal-related correction dose will be calculated by dividing the interstitial glucose reduction by the time it takes to recover ( $<180$  mg/dL) from hyperglycemia after the correction dose. If within 4 hours a second correction bolus is given, only the first non-meal-related correction bolus time will be used. If the glucose never recovers to  $<180$  mg/dL within 4 hours, the glucose rate will be calculated by dividing the greatest glucose reduction within 4 hours by the time it takes to reach this level.

The glucose reduction rate will be analyzed by a MMRM model. The MMRM model will include the fixed effects of treatment, period, and sequence as fixed effects and patient as a random effect. The interstitial glucose reduction rate will also be analyzed by sub-intervals of interstitial glucose levels at the time of the non-meal-related correction bolus: 180 to 250, 250 to 300, and >300 mg/dL (10 to 13.9, 13.9 to 16.7, and >16.7 mmol/L).

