6.11.7.4. Hepatobiliary Events

6.11.7.4.1. Treatment-Emergent Potential Hepatic Disorder

The percentages of patients with treatment-emergent drug-related hepatic disorder events will be summarized and compared by treatment group using MedDRA PT nested within each SMQ, and ordered by decreasing frequency. The following SMQs based on MedDRA will be used to identify potential hepatic disorders:

- Broad and narrow terms in the Liver related investigations, signs and symptoms SMQ (20000008)
- Broad and narrow terms in the Cholestasis and jaundice of hepatic origin SMQ (20000009)
- Broad and narrow terms in the Hepatitis non-infections SMQ (20000010)
- Broad and narrow terms in the Hepatic failure, fibrosis and cirrhosis and other liver damage SMQ (20000013)
- Narrow terms in the Liver-related coagulation and bleeding disturbances SMQ (20000015)

The percentage of patients with any 1 of the terms will be summarized, in addition to the percentages for each MedDRA PT. The percentages of patients with potentially drug-related hepatic disorders that lead to permanent study discontinuation will be summarized similarly.

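### Discontinuation due to an AE is compared with Prescott's exact test, but a patient who stops in Period I has no Period II outcome and the plan does not say how that patient enters the test

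*SAP*

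**What the plan says.** SAP 6.11.5 groups patients with SAEs together with those "who discontinued from the study due to an AE will be summarized using MedDRA Preferred Term (PT) nested within System Organ Class (SOC"), and then states: "Prescott's exact test will be performed for treatment comparison". Protocol 10.3.3.2 covers SAEs, AEs given as the reason for stopping, and TEAEs in one sentence; the proportions with an event are to be "summarized and compared between treatment groups using Prescott's test".

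Protocol 8.1 states: "Patients who need to discontinue from study treatment will also be discontinued from the Study". SAP 6.11.4 repeats the rule: "patients who discontinue the IP prematurely are required to discontinue from the study".

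On incomplete data, SAP 6.3 relies on the MMRM for continuous variables and otherwise refers to Sections 6.11 to 6.13. Section 6.11.5 has no rule for a patient with only one period. The restriction to patients dosed in both periods is written in SAP 6.11.1 for the primary Wilcoxon test. SAP 6.11.2 applies the primary-endpoint approach to a list of pump-related endpoints and severe hypoglycemia. AE analyses use the Safety Population and all data regardless of IP use (SAP 6.1 and Table ITSI.6.5).

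For hepatic events, SAP 6.11.7.4.1 says that "hepatic disorders that lead to permanent study discontinuation will be summarized similarly" and names no test of its own. Prescott's test would apply there only through the general default in SAP 6.1.

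**The concern.** Prescott's test suits an event that a patient can have, or not have, in each of two periods. Stopping for an AE is different: it ends participation. A patient who stops in Period I never receives the second insulin, and a patient observed in both periods cannot have stopped in Period I. A within-patient test therefore has nothing to compare for the first randomized exposure, where intolerance would first appear.

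The trial is meant to assess safety comparability, and stopping for an AE is a main tolerability outcome. The plan attaches a p-value to it, yet two programmers following the same text could obtain very different values from the same data. A p-value of 1 printed beside a visible imbalance could also be misread as evidence of no difference.

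**Working it through.** **Plan's own figure.** 42 completers at 12% dropout: 42 / 0.88 = 47.7, rounded up to 48, or 24 per sequence. This matches Protocol 10.1 and SAP 5.2. Expected all-cause dropout is 0.12 × 48 = 5.8, about 6. The documents give no AE-discontinuation rate, so the counts below are assumptions.

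**What the test becomes.** Score each patient −1 (event in Period I only), 0 (no difference) or +1 (event in Period II only), and compare the scores between sequences exactly. Among patients with both periods, −1 cannot occur for this endpoint. The test then reduces to Fisher's exact test on Period II stops between sequences. The calculation confirmed identical p-values in every case tried.

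**Case 1: six LY900014 stops in Period I (Sequence A), no others.**
- One-period patients dropped: no events remain, so p = 1.0.
- Period II coded as no event: p = 2 × C(24,6)/C(48,6) = 2 × 134,596/12,271,512 = 0.022. This equals Fisher's test on Period I.
- With stoppers kept, 5 vs 0 gives p = 0.0496 and 4 vs 0 gives p = 0.109. With stoppers dropped, both give 1.0.

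**Case 2: three LY900014 stops in each period, none on lispro.** Period I is 3/24 vs 0/24. Period II is 3/24 (Sequence B, on LY900014) vs 0/21 (Sequence A, on lispro).
- One-period patients dropped: p = [C(24,3) + C(21,3)]/C(45,3) = (2,024 + 1,330)/14,190 = 0.236.
- Period II coded as no event: p = 2 × C(42,21)/C(48,24) = 0.033.

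**Exact conditional test stratified by period.** Condition on the number of stops in each period, among patients dosed in that period.
- Case 1: only Period I contributes, so p = 0.022.
- Case 2, all six on LY900014: (2,024/17,296) × (2,024/14,190) = 0.1170 × 0.1426 = 0.0167. All six on lispro: (2,024/17,296) × (1,330/14,190) = 0.1170 × 0.0937 = 0.0110. Two-sided p = 0.028.

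| LY900014 stops (Period I, Period II); none on lispro | Prescott, one-period patients dropped | Prescott, Period II coded no event | Fisher, Period I only | Exact, stratified by period |
|---|---|---|---|---|
| 6, 0 | 1.0 | 0.022 | 0.022 | 0.022 |
| 3, 3 | 0.236 | 0.033 | 0.234 | 0.028 |
| 0, 6 | 0.022 | 0.022 | 1.0 | 0.022 |

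**Power under assumed risks.** Per-period risk of an AE stop is 2% on lispro; 4,000 simulated trials per row. About half of all AE stops (50% to 51%) are lost when one-period patients are dropped.

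| LY900014 risk | Power, dropped | Power, kept as no event |
|---|---|---|
| 5% | 0.4% | 1% |
| 10% | 4% | 18% |
| 15% | 12% | 48% |
| 20% | 24% | 74% |
| 25% | 39% | 90% |

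**The case against.** The exclusion is nowhere stated for AEs. The both-periods wording belongs to the primary test and, through SAP 6.11.2, to listed secondary endpoints. The AE analysis set is the whole Safety Population, which includes one-period patients. A reader might infer that the plan definitely drops every Period I stopper and will return p = 1.0. The text does not support that as a certainty: p = 1.0 depends on one of two unstated codings. This objection stands. It does not remove the problem, because the analysis set cannot supply a Period II outcome for someone who has left, and the alternative coding is not in the plan either.

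A reader might also infer that an imbalance would be hidden. It would not. Period I stoppers appear in the disposition tables by sequence and period (SAP 6.6), in the AE overview, the counts by treatment group and the listing (SAP 6.11.5), and in a narrative for each case (SAP 6.11.12).

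The six-versus-none case is an extreme one: it assigns all the planned dropout to AEs on LY900014 in Period I. At 5% against 2%, power is negligible either way. The test is also planned within preferred term and organ class, where even fewer stops would share a term. The trial is not powered for superiority or non-inferiority, and these tests carry no multiplicity control. All of this limits the consequence; none of it makes the test fit the endpoint.

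**Conclusion.** The concern holds in this form: Prescott's test does not fit an outcome that ends participation, and the plan leaves open how a one-period patient enters it. Dropping such patients loses all Period I AE stops. Coding Period II as event-free keeps them, but treats a patient who was not at risk as having tolerated the other insulin. On the same assumed data the choice moves p from 1.0 to 0.022 (six stops in Period I) or from 0.236 to 0.033 (three in each period).

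The effect is on the p-value only, and its size rests on assumed counts and risks. For SAEs and other TEAEs the loss is partial, limited to patients who leave before Period II. The matter deserves correction before unblinding, but it does not threaten the primary analysis or the descriptive safety reporting.

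**What to change.** - In SAP 6.11.5, replace Prescott's test for AE-related discontinuation by an exact conditional test of LY900014 against lispro stratified by period, with patients dosed in that period as the denominator. Show counts and a 95% CI for the risk difference by period.
- Note the departure from Protocol 10.3.3.2 in the SAP, as SAP 6.1 allows for changes that do not alter a principal feature.
- If hepatic discontinuations (SAP 6.11.7.4.1) are compared, use the same test.
- For the remaining Prescott tests, state that only patients dosed in both periods enter, and report events in one-period patients alongside.

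A Fisher test on Period I alone is a tempting simpler remedy, but it has the mirror-image gap: six stops all in Period II would give p = 1.0, and three in each period would give 0.234.

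The cost is SAP wording and one more table. The limitation is that Period II is compared only among patients who remained after Period I, so that stratum is no longer the full randomized comparison; the by-period display makes this visible.
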